10 DEVIATIONS FROM THE CLINICAL INVESTIGATION PLAN AND CLINICAL INVESTIGATION PLAN VIOLATIONS

The Investigator is not allowed to deviate from the CIP, except in an emergency.

10.1 Deviations

A deviation is a planned departure from the requirements of the CIP in order to deal with unforeseen circumstances.

Non-emergency Deviations: In the event of a non-emergency deviation, prior approval by the Sponsor is required. If the deviation may affect the rights, safety, or welfare of participants or the scientific

Protocol Version 2.1, 27 Jun 2019

LINK Medical Research | Protocol template

Version 2.0 | Effective date 17Apr2018

integrity of the clinical investigation, IEC approval is also required prior to implementation.

Emergency Deviations:

Emergency deviations required for the safety and welfare of the patient will be implemented by the Investigator and notified to the Sponsor as soon as possible after implementation.

The Sponsor is responsible for analyzing deviations and assessing their significance. Corrective action will be implemented to avoid repeated deviations, which may include suspending the clinical investigation and/or amending the CIP.

10.2 Clinical Investigation Plan Violations

Clinical Investigation Plan violations are deviations made without permission as a result of error or fraud/misconduct. Where the Monitor or Sponsor identifies that the Investigator is out of compliance, this will be notified to the Investigator in writing, with a request to correct the source of the deviation immediately. Corrective action will be implemented to avoid repeated non-compliance, which will usually include re-training and may include terminating the clinical investigation at the site.

10.3 Reporting of Deviations and Clinical Investigation Plan Violations

Depending on the nature of the deviation, they will either be recorded by the Investigator on the eCRF or documented by the Monitor and signed by the Investigator. Emergency deviations and violations which may affect the rights, safety or welfare of participants; or the scientific integrity of the clinical investigation will be notified to the IEC as soon as possible after the Sponsor has become aware of them.

11 SPECIAL REQUIREMENTS AND PROCEDURES

11.1 Good Clinical Practice

This clinical investigation will be conducted in accordance with Note for Guidance on Good Clinical Practice: CPMP/ICH/135/95, January 1997 (where applicable to medical devices) and the principles of the European Standard EN ISO 14155:2011 Clinical Investigation of Medical Devices for Human Patients – Good Clinical Practice.

11.2 Ethics

11.2.1 Institutional Ethics Review

The final CIP, including the final version of the patient information and consent form, must be approved or given a favorable opinion in writing by an IEC before enrollment of any patient into the investigation. The Investigator is responsible for informing the IEC of any amendment to the CIP as per local requirements.

11.2.2 Ethical Conduct of the Clinical Investigation

The clinical investigation will be conducted in compliance with applicable regulatory requirements and with the ethical principles of the latest revision of the Declaration of Helsinki as adopted by the World Medical Association ([Appendix 2](#)).

11.2.3 Patient Information and Consent

All patients will receive written and verbal information regarding the investigation prior to any investigation-related procedures. This information will emphasize that the participation in the investigation is voluntary and that the patient may withdraw from the investigation at any time and for any reason. All patients will be given the opportunity to ask questions about the investigation and will be given sufficient time to decide whether to participate in the investigation.

Before any clinical investigation-related procedures are undertaken, the ICF will be signed and dated by the patient (or their legally acceptable representative and/or witness, as applicable) and by the Investigator, or the qualified designee who gave the patient the verbal and written information.

If any data is transferred to EEA countries outside Sweden, the data will not identify any persons taking part in the clinical investigation in accordance with the EU General Data Protection Regulation (GDPR).

11.3 Patient Protection Procedures

11.3.1 Procedures in Case of Medical Emergency

The Investigator is responsible for ensuring that procedures and expertise are available to cope with medical emergencies during the clinical investigation.

11.3.2 Patient Data Protection

The written patient information explains that the data will be stored in a computer database, maintaining confidentiality in accordance with national data legislation, and that authorized representatives of the investigational site, Sponsor, RA, or an IEC require access to those parts of the medical records relevant to the clinical investigation, including medical history, for verification of data and appropriate conduct of the clinical investigation.

Confidentiality of patient data will be maintained at all times. Patient anonymity will be guaranteed and documentation relating to a patient will be kept in a secure location.

11.3.3 Insurance

The Sponsor has arranged the appropriate product liability and clinical trials insurance to cover the requirements of this clinical investigation.

11.4 Report and Publication

A final report of the investigation (a “Clinical Investigation Report” [CIR]) should be completed, even if the investigation is prematurely terminated. The report will be prepared by the Sponsor according to the guideline presented in Annex C of ISO 14155-1:2011(E).

All publications and presentations must be based upon the CIR.

Protocol Version 2.1, 27 Jun 2019

LINK Medical Research | Protocol template

Version 2.0 | Effective date 17Apr2018

All information supplied by the Sponsor in connection with this investigation will remain the sole property of the Sponsor and is to be considered confidential information. No confidential information will be disclosed to others without obtaining prior written consent from the Sponsor and will not be used except in the performance of this investigation.

The Investigator may publish results from this investigation; however as some of the information regarding the investigational medical device and development activities may be of a strictly confidential nature, the Sponsor must first be given the opportunity to review any publication manuscript prior to submission to journals, meetings or conferences.

The Sponsor may choose to publish or present data from this investigation. If an Investigator is offered first authorship, he/she will be asked to comment and approve the publication. The author order will be determined out of number of completed subjects. The Sponsor has the right to use the results for registration and internal presentation and for promotion.

11.5 Confidentiality

All processing of personal data will be stored confidential and handled according to legislations concerning the protection of personal data. Patients will be identified only by code. The informed consent form shall contain information about what personal data to be collected in the study and that this will be kept confidential. The provided information shall be sufficient to enable all subjects to give their consent not only to the participation in the study, but also to the processing of personal data. See also [Section 11.3.2](#).

12 CLINICAL INVESTIGATION TIME TABLE AND TERMINATION

Clinical investigation start (first patient first visit): Q4 2018

Inclusion completed (last patient first visit): Q1 2019

Last patient out (last patient last visit): Q2 2019

Appendix 1 Patient Questionnaire

Section 1. Bacterial Vaginosis Symptoms

Day(s) 0, 4, 7, 14, and 35; or Day(s) 0, 4, 7, 11, 14, 21 and 42 if receiving prolonged treatment. Questions will be asked by the Investigator at Day(s) 0, 7, and 14 (for patients receiving prolonged treatment); and by the Clinical Trial Unit at remaining days.

Scoring of symptoms

	0 = none (absent)	1 = mild (slight)	2 = moderate (definitely present)	3 = severe (marked, intense)
Irritation				
Fishy smell				
Burning				

The question “Have the symptoms returned, so that you need to seek medical care?” (yes/no) will be asked at Day(s) 14 and 35 if not receiving prolonged treatment and at Day(s) 21 and 42 if receiving prolonged treatment.

Section 2. Usability

Day 7, and Day 14 if receiving prolonged treatment:

Is the vaginal tablet easy to use?

- Yes
- No
- If no, provide reason: _____

Do you find the use of the vaginal tablet gentle?

- Yes
- No
- If no, provide reason: _____

Is the treatment odor free?

- Yes
- No

Is the treatment smear-free and dripless?

- Yes
- No

How do you generally regard the treatment?

1	2	3	4	5	6	7	8	9	10
Not satisfied					Very satisfied				

Section 3. Concomitant Medications

At Day(s) 4, 7, 14, and 35; or Days(s) 4, 7, 11, 14, 21, and 42 if receiving prolonged treatment; patients will be asked: “since the last study visit or telephone contact, have you changed dose or taken any new medication?”

Section 4. Adverse Events

The following question will be asked at each patient contact: “since the last visit / telephone contact, have you had any health problems?”

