Current recommended first-line treatments for BV are oral or topical metronidazole and topical clindamycin.²² Initial cure rates are usually 70% to 80% and recurrence rates are high (Table 1). Metronidazole interacts with many other drugs and concomitant alcohol intake is advised against.²³ The recommended treatment for BV in pregnant women is oral metronidazole or oral clindamycin; topical treatments are not recommended for women at high risk of preterm birth or obstetric complications, due to not having the same effect as oral treatment in preventing BV-associated preterm birth.²⁴ Other antibiotic treatments include oral secnidazole²⁵ and vaginal rifaximin,²⁶ but these are not included as recommended treatments in most clinical guidelines. The U.S. Food & Drug Administration (FDA) approved secnidazole in 2017 for the treatment of BV but it is not approved for use in BV in Europe.

In the absence of effective therapies and in an attempt to treat recurrent symptoms, some women resort to self-treatment remedies, such as oral or vaginal yoghurt, antiseptic creams, over-the-counter (OTC) antimycotics, wearing cotton underwear, and douching. These most often have limited effect, and douching is even associated with a higher incidence of BV.²

Taken together, there remains an unmet medical need for novel treatment and prevention options for patients with BV, especially treatments targeting vaginal biofilms, while allowing beneficial microbes to thrive.

Table 1 Cure Rates and Recurrence of Antibiotic Therapies for Bacterial Vaginosis

Therapy	Duration of Treatment	Clinical Cure Rate (%)	Recurrence Rate	Ref.
Metronidazole, oral	Twice daily, 5-7 days	40-90	>50% within 12 months	9,14,16,24,27
Metronidazole, gel	Once daily, 5 days	30-80	>50% within 12 months	9,14,16,27
Clindamycin, oral	Twice daily, 7 days			
Clindamycin, cream	Once daily, 5 days	33-90	9-30% after 4 weeks. >50% within 12 months	9,14,24,27
Tinidazole, oral	Twice daily, 7 days	70-100	20-40% 2 months after treatment	16,27
Dequalinium, suppository	Once daily, 6 days	81.5		27
Secnidazole*	Single dose	52-68		25
Rifaximin, intravaginal	Not reported	26-46		16

*Phase II Study

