2.2 Secondary Objectives

To further investigate the clinical performance of the investigational product.

Secondary endpoints:

All patients

- Proportion of patients being negative for each of the 3 Amsel criterion on Day 7 compared to Day 0
- Proportion of patients having a reduction in the sum of the 3 BV symptoms scores (fishy smell, burning, and irritation) on Day 4 and Day 7, compared to Day 0
- Change in the sum of the 3 BV symptoms scores (fishy smell, burning, and irritation) from Day 0 to Day 4 and Day 7
- Usability, measured by patient questionnaire

For patients not receiving prolonged treatment

- Recurrence rate on Day 14 and Day 35, defined as the proportion of patients clinically cured on Day 7 and thereafter responding “yes” to a yes/no question from the patient questionnaire on whether the symptoms have recurred

For patients receiving prolonged treatment

- Proportion of patients receiving prolonged treatment
- Clinical cure rate on Day 14, defined as the absence of all of the 3 Amsel criteria as defined above
- Proportion of patients being negative for each of the 3 Amsel criterion on Day 14 compared to Day 0
- Proportion of patients having a reduction in the sum of the 3 BV symptoms scores (fishy smell, burning, and irritation) on Day 11, Day 14, Day 21, and Day 42, compared to Day 0
- Change in the sum of the 3 BV symptoms scores (fishy smell, burning, and irritation) from Day 0 to Day 11, Day 14, Day 21, and Day 42

- Recurrence rate on Day 21 and Day 42, defined as the proportion of patients clinically cured on Day 14 and thereafter responding “yes” to a yes/no question from the patient questionnaire on whether the symptoms have recurred
- Proportion of patients receiving rescue treatment on Day 14

Exploratory endpoint variables:

All patients

- Effect on vaginal microbiome on Day 0 and Day 7
- Vaginal pH on Day 7

For patients not receiving prolonged treatment

- Effect on vaginal microbiome on Day 35

For patients receiving prolonged treatment

[figure not shown]
- Effect on vaginal microbiome on Day 14 and Day 42

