3.5.9 Day 14 (± 2 Days); Follow-up Telephone Contact

Applicable to patients NOT receiving prolonged treatment

Patients not receiving additional doses of investigational product on Day 7 will be contacted by the Clinical Trial Unit by telephone on Day 14. Patients will be asked questions from the patient questionnaire about BV symptoms (fishy smell, irritation, and burning), recurrence, concomitant medications, and AEs, if any.

Procedures performed:

- Bacterial vaginosis recurrence
- Symptoms of BV (fishy smell, irritation, and burning) evaluated by patients according to a scoring scale (0-3)

- Recording of:
 - concomitant medications, and
 - adverse events

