8.8 Recurrence rate

Recurrence rate is based on a binary variable, where a recurred patient is defined as a patient clinically cured on Day 7 and thereafter responding "yes" at specified follow-up visits to a yes/no question from the patient questionnaire on whether the symptoms have recurred.

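### Recurrence is defined as return of symptoms, but the only question asked also requires a need for medical care, so the reported rate can only equal or understate recurrence as defined

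*Protocol*

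**What the plan says.** Protocol 2.2 lists recurrence as a secondary endpoint, at Days 14 and 35 for women without prolonged treatment and at Days 21 and 42 for women with it. A recurrence is a clinically cured woman who afterwards says yes to a "yes/no question from the patient questionnaire on whether the symptoms have recurred". The synopsis and protocol 6.1 repeat this, as do SAP 3.2.1 and 7.9.2 (endpoints vi and xi). SAP 8.8, which derives the variable, counts a yes "at specified follow-up visits to a yes/no question from the patient questionnaire on whether the symptoms have recurred".

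The item actually put to patients is in Section 1 of the questionnaire (protocol Appendix 1): "Have the symptoms returned, so that you need to seek medical care", answered yes or no. It "will be asked at Day(s) 14 and 35 if not receiving prolonged treatment and at Day(s) 21 and 42 if receiving prolonged treatment". The questionnaire has no other recurrence item.

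At the same calls the women score irritation, fishy smell and burning from 0 to 3. SAP 7.9.2 presents these scores and their sum descriptively, but no recurrence rule uses them. For women without prolonged treatment, the symptom-score endpoints stop at Day 7. The recurrence rates are reported with two-sided 95 % Clopper-Pearson intervals and are not tested.

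**The concern.** The endpoint definition and the question describe different events. The definition asks for symptoms that have come back. The question asks for symptoms that have come back and that also create a need for care. The scale in the same questionnaire section allows mild symptoms, or moderate and definitely present ones, alongside a truthful no. The results would then carry the label of symptom recurrence while measuring something narrower.

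This matters because protocol 1.1 presents high recurrence as a main part of the unmet need. For women cured on Day 7, it is also the only secondary performance endpoint after treatment. They have no further Amsel examination (protocol Table 2), and the Day 35 microbiome is exploratory. SAP 7.11, which lists changes and clarifications, does not mention the difference in wording.

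**Working it through.** The plan assumes no recurrence rate, so there is no figure to reproduce. The check is a comparison of texts, then a point of logic, then an illustration.

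**1. Texts side by side**

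| Place | Condition for a recurrence |
|---|---|
| Protocol 2.2, 6.1; SAP 3.2.1, 7.9.2, 8.8 | Cured, then yes to symptoms having recurred |
| Protocol Appendix 1, Section 1 | Yes to symptoms having returned **and** a need to seek care |

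**2. Direction**

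Let R be return of symptoms and C a need for care. The definition targets P(R). The item, answered as worded, gives P(R and C). Since (R and C) is contained in R, P(R and C) ≤ P(R), with equality only if every woman with returned symptoms needs care. The rate can therefore not exceed the defined endpoint and may fall below it.

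**3. Illustration of size**

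Let s be the share of symptom returns judged to need care. Then reported rate = s × true rate. The documents do not give s or the true rate, so both are assumptions.

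| True rate | s = 0.90 | s = 0.75 | s = 0.50 | s = 0.25 |
|---|---|---|---|---|
| 30 % | 27 % | 22.5 % | 15 % | 7.5 % |
| 20 % | 18 % | 15 % | 10 % | 5 % |

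In counts, the sample-size section (protocol 9.3) assumes 70 % cured and includes 24 patients: 0.70 × 24 = 16.8, taken as 17 cured on Day 7. Suppose symptoms return in 5 of them.

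| Of the 5, needing care | Reported rate | 95 % Clopper-Pearson interval |
|---|---|---|
| 5 | 5/17 = 29.4 % | 10.3 to 56.0 % |
| 4 | 4/17 = 23.5 % | 6.8 to 49.9 % |
| 3 | 3/17 = 17.6 % | 3.8 to 43.4 % |
| 2 | 2/17 = 11.8 % | 1.5 to 36.4 % |

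**4. Context for these figures**

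Day 35 is 35 − 6 = 29 days after the last dose for women treated once. Protocol Table 1 gives 9–30 % recurrence after 4 weeks for clindamycin cream. The illustrated rates run from near the top of that range to near the bottom. The plan specifies no such comparison, but a reader could make one. The intervals overlap widely, so with these numbers sampling error is at least as large as the shift shown.

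**The case against.** The strongest reply is that the definition points to the questionnaire, so anyone can look up what was asked. Recurrence is an untested secondary endpoint in a feasibility study, and the primary conclusion does not depend on it. All of that stands and limits the weight of the point. It does not reconcile the label with the item, because a reader of the results will see only the label.

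Several stronger readings are tempting, and the documents do not support them:

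- **A material bias has been shown.** Only the direction follows from the wording. The size rests on invented inputs and could be zero.
- **Many recurrences will be missed because women treat themselves.** Protocol 1.1 says only that "some women resort to self-treatment remedies". It also describes recurrence as often leading to repeated antibiotic treatment, which suggests care-seeking. Over-the-counter medication is recorded too (protocol 5.7).
- **Returned symptoms will be invisible.** The Day 14 and Day 35 scores are presented descriptively, and there is an exploratory Day 35 microbiome endpoint. The scores are simply not linked to recurrence.
- **True BV recurrence is understated.** Neither question confirms BV by Amsel criteria. Irritation and burning can have other causes; protocol 1.3.2 reports vaginal itching as the commonest adverse event with a comparable pessary. The direction against confirmed BV is therefore open.
- **The comparison favours the pessary.** With one arm there is no contrast to bias. The most that can be said is that the absolute rate may look better than symptom recurrence as defined.

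**Conclusion.** The point holds as a mismatch between endpoint and item. If women answer the question as worded, the reported rate equals or understates symptom recurrence as the protocol and SAP define it. It falls below whenever symptoms return without a need for care. The documents do not allow the shortfall to be estimated, and the 29.4 % to 11.8 % example is only an illustration on stated assumptions. Confidence is high about the wording and the direction, and there is none about the size. The mismatch should be corrected because it changes what a reported rate means. The primary endpoint and the sample size are not affected.

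**What to change.** In Appendix 1, replace the single item with two:

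- (a) *Have the symptoms returned?* (yes/no). This answer defines recurrence in protocol 2.2 and SAP 8.8.
- (b) *If yes, do you need to seek medical care?* (yes/no). This is reported separately.

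Protocol section 12 foresaw the last patient out in Q2 2019, so calls may already have been made with the single item. In that case, change SAP 8.8 instead:

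- Rename the endpoint *recurrence of symptoms needing medical care*.
- Add a prespecified supportive analysis of symptom return from the 0–3 scores for all three symptoms at Days 14 and 35, and at Days 21 and 42. One possible rule is a sum score higher than at the cure visit (Day 7, or Day 14 after prolonged treatment). The threshold is a choice and should be fixed before the data are examined.
- Cross-tabulate the scores against the yes/no answer at each call, so that women with symptoms who answered no can be counted.

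The cost is one extra questionnaire line, or one revised SAP definition and one table. Neither route adds a visit or procedure, and the fallback needs no new data. The downside for the sponsor is that the symptom-recurrence rate may be less favourable than the rate from the single item.

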1.3.2 Clinical Data

The GDL-and-NaG-containing investigational device, *Gedea Pessary* (commercial name *pHyph*), has not been tested in previous clinical trials. Products containing polymerized lactic acid have comparable properties to Gedea Pessary, as lactic acid and GDL have the same ability to inhibit bacterial biofilm formation and lower the pH to a similar extent, see IB. One such product, *Laccure Pessary* (Laccure AB, Helsingborg, Sweden), is buffered to pH 3.5, whereas Gedea Pessary is buffered to pH 3.6. Laccure Pessary has been tested in a clinical trial of 126 patients with confirmed BV, where 93 patients were treated with 1 or 2 doses of Laccure Pessary and 33 patients formed the control group.³⁸ The study showed an 80% cure rate for the single-dose treatment. Most adverse events (AEs) reported were of mild intensity and brief. The most common event was vaginal itching, experienced less than 20% of patients. No serious adverse events (SAEs) occurred and the treatment had no visually detectable negative impact on the vaginal mucosa.

Based on published studies on current treatments for BV, oral, topical, and intravaginal antibiotics are generally well tolerated; reported AEs include nausea, headache, diarrhea, vaginal discharge, and vulvovaginal pruritus. The reported frequencies of AEs after treatment with antibiotics are between 4.6% to 42%, depending on antibiotic used and route of administration.^{16,25,27,39}

Collectively, pre-clinical data indicate that GDL and NaG are safe and may be an effective topical treatment for BV, and a GDL-and-NaG-containing slow-release pessary is to be investigated in this clinical trial.

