2 STUDY OBJECTIVES

2.1 Primary Objectives

To investigate the clinical performance, tolerability, and safety of the investigational product.

Primary endpoints:

- Clinical cure rate on Day 7
 - Defined as absence of all of the following Amsel criteria:
 1. Thin, white, yellow, homogenous discharge
 2. Clue cells on microscopy (more than 20% of epithelial cells)
 3. Release of fishy odor “i.e. a positive whiff test” when alkali (10% potassium hydroxide [KOH] solution) is added
- Safety and tolerability, based on reported treatment-emergent AEs

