3.2.1 Risks and Benefits

The investigational device, Gedea Pessary has been evaluated in accordance with ISO 10993 (Biological Evaluation of Medical Devices). The evaluation included: cytotoxicity testing (Direct cell contact test, ISO 10993-5); *in vivo* irritation (Vaginal acute irritation; ISO 10993-10); and sensitization (local lymph node assay, ISO 10993-10). The *in vitro* cytotoxicity test, classified the test item as slight to moderate cytotoxic (scale 1–2 on a 3-grade scale); the *in vivo* irritation test as well as the *in vivo* sensitization test showed no signs of irritation, necrosis, or sensitization after treatment with Gedea Pessary.

The vaginal pessary may, in similarity with other vaginally administered products, cause temporary minor discomfort at insertion. The vaginal sampling procedures are similar to sampling procedures used in clinical practice and are unlikely to cause any major inconvenience to patients. In the Laccure pessary study,³⁸ there were no SAEs and vaginal itching was the most common AE.

There is a risk that patients will have no clinical benefit from the investigational device. This may cause patients to experience symptoms of BV including vaginal fishy smell, burning or irritation, pain during sexual intercourse, pain or discomfort when urinating, or abnormal vaginal discharge longer than necessary. However, an antibiotic will be offered on Day 14 if any symptoms should still be present, thus avoiding any risk associated with long-term untreated BV.

Subjects included in the study must refrain from using other intravaginal products to mitigate any risk of interactions with concomitant vaginally-administered products. The investigational

^a And on Day(s) 7, 9, 11, and 13 if receiving prolonged treatment

Protocol Version 2.1, 27 Jun 2019

LINK Medical Research | Protocol template

Version 2.0 | Effective date 17Apr2018

device acts locally on the vaginal mucosa and most likely will most likely not affect any concomitant systemic treatment.

Taken together, as the anticipated levels of discomfort are transient and mild, and that risks associated with long-term untreated BV are avoidable, the use of the investigational product appears to offer clinical benefits at a reasonable risk level.

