7.6 Capturing and Reporting of Untoward Medical Events / Adverse Events

Patients shall be asked about AEs at all visits (both site visits and telephone contacts). Questions for collecting AEs are specified in [Appendix 1, Section 4](#).

Adverse events can also be obtained from:

- Signs and symptoms from patient examinations,
- Laboratory values, or
- Spontaneous reports by subjects or their relatives.

All AEs and ADEs, will be captured in the section for AEs in the eCRF or in case of serious events in the section for SAEs, SADEs, or USADEs.

All events fulfilling the definition of untoward medical event will be captured and reported from the time when the participant signs the ICF and to the last visit in the study or until the participant has left the study. Untoward medical events may need follow-up after the last visit in the study before being rated as recovered or given a final status according to the definitions above.

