7.9.1 Primary endpoints

- Clinical performance endpoint: Clinical cure rate on Day 7 will be calculated and presented together with a one-sided 95 % confidence interval based on the exact binomial distribution (Clopper-Pearson).
- Clinical safety endpoint: Safety and tolerability will be assessed according to Section 7.10.2.

The primary clinical performance endpoint is the Clinical cure rate on Day 7, where clinical cure is defined as the absence of all of the Amsel criteria stated in [Section 3.1.1](#) above. The primary performance objective of the trial is to show that the Clinical cure rate is above 40 %, *i.e.* to show that the lower limit of the one-sided 95 % CI for the observed cure rate is above 40 %.

Hypotheses for the primary clinical performance endpoint

Null hypothesis: Clinical cure rate is less than or equal to 40 %.

Alternative hypothesis (one-sided): Clinical cure rate is above 40 %.

The primary clinical safety endpoint, i.e. safety and tolerability based on reported treatment-emergent AEs, will be analysed descriptively only, see Section 7.10.2 below, and will thus not be connected to any formal hypothesis testing.

7.9.2 *Secondary clinical performance endpoints*

The secondary clinical performance endpoints are either binary or continuous.

The usability data, as measured by the patient questionnaire and which contain both binary and continuous endpoints, will only be presented descriptively.

The other binary secondary clinical performance endpoints will be calculated and presented together with a two-sided 95 % confidence interval based on the exact binomial distribution (Clopper-Pearson). No hypothesis testing will be made on the binary endpoints.

The only remaining clinical performance endpoint that is considered as a continuous endpoint is the change in the sum of the 3 BV symptoms scores. Here, applying Student's t distribution, a two-sided 95% confidence intervals for the arithmetic mean will be presented.

Hypothesis for the continuous secondary clinical performance endpoint "Change in the sum of the 3 BV symptoms scores"

Null hypothesis: Change from baseline is = 0.

Alternative hypothesis (two-sided): Change from baseline \neq 0.

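### Tolerability has no solicited local-reaction item, and neither raised symptom scores nor usability reasons have a stated route to AE review, so mild local reactions may be under-recorded

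*Protocol*

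**What the plan says.** Protocol 2.1 makes the second co-primary endpoint "Safety and tolerability, based on reported treatment-emergent AEs". Protocol 7.10 (Tolerability) and 9.2.3.1 (Local Tolerability) add no instrument of their own and refer only to AEs.

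For the questions that collect AEs, Protocol 7.6 points to Appendix 1, Section 4. That section holds one question, put at every contact: "since the last visit / telephone contact, have you had any health problems". Section 7.6 also allows AEs to come from "Signs and symptoms from patient examinations", laboratory values and spontaneous reports, and requires every qualifying event to be captured. Protocol 7.5.2 adds that a doubtful observation should be reported.

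The protocol says which local effects it has in mind. On the comparable lactic acid pessary, section 1.3.2 reports: "The most common event was vaginal itching, experienced less than 20% of patients". Section 3.2.1 says the study pessary may "cause temporary minor discomfort at insertion".

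Two other parts of the questionnaire touch on local complaints:

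- Appendix 1, Section 1 scores irritation, fishy smell and burning from 0 to 3 at each contact. These are BV symptoms, and their sum feeds secondary performance endpoints.
- Appendix 1, Section 2 asks on Day 7 (and Day 14 if treatment is prolonged) "Do you find the use of the vaginal tablet gentle", with space for a reason if the answer is no. SAP 7.9.2 states that usability data "will only be presented descriptively".

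**The concern.** A tolerability endpoint built on AEs is only as good as the way AEs are elicited. A woman already seeking care for vaginal symptoms may not regard brief itching or discomfort at insertion as a health problem, and nothing in the script mentions either. If she does mention pain, it may be as the reason why the tablet was not gentle, and that answer is filed under usability.

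Three features raise the stakes. The pessary has not been tested clinically before (Protocol 1.3.2). There is no control arm in which the same elicitation gap would show. And Protocol 9.1 and SAP 7.1.7 require both co-primary endpoints to be favourable while giving no numeric criterion for this one, so each mild reaction that goes unrecorded makes the result look better.

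**Working it through.** The plan gives no target, threshold or expected rate for tolerability, so there is no figure of its own to reproduce. The check has two parts: reading the collection routes side by side, and a small illustration.

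**Routes by which a mild local reaction could become an AE**

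| Route | Where | Asks about local reactions? | Stated link to AE data? |
|---|---|---|---|
| Open question | Protocol 7.6; Appendix 1, Section 4 | Not specifically | Yes |
| Examination findings | Protocol 7.6 | No; examinations are on Day 0 and Day 7 (plus Day 14 if prolonged) and assess Amsel criteria | Yes |
| Laboratory values | Protocol 7.6 and 7.2 | No; the work is culture, sequencing and pH | Yes |
| Spontaneous report | Protocol 7.6 | No | Yes |
| Irritation and burning scores | Appendix 1, Section 1 | Yes, but not itching or insertion discomfort | None stated |
| Usability reasons | Appendix 1, Section 2 | Indirectly | None stated |

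The routes that lead to the AE page do not ask about local reactions, and the two that come closest to asking have no stated route to that page. The SAP does write a cross-reporting rule for one other source: under 7.10.2, a device event that is also an AE must be reported as one too. No equivalent exists for usability reasons or symptom scores.

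The performance analysis does not fill the gap. It uses the sum of the three scores (range 0 to 9), and SAP 8.7 counts any negative change as a reduction. A constructed example: Day 0 smell 3, burning 0, irritation 0 gives 3; Day 7 smell 0, burning 1, irritation 1 gives 2. The change is 2 − 3 = −1, a reduction, although burning and irritation are both new. SAP 7.9.2 tabulates the single items descriptively, so the rise would be visible there, but no rule says when it should be assessed as an AE. Protocol 7.3 excludes conditions known at consent and does not say how worsening of such a condition is treated.

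**Illustration of size**

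Inputs: N = 24 (Protocol 9.3); true local-reaction rate p; fraction c of affected women whose reaction is recorded. The 20 % value of p is the ceiling quoted for the comparable pessary. The 10 % value and every value of c are assumptions.

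Expected women recorded = 24 × p × c. Chance that none is recorded = (1 − p × c)^24.

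| p | c | p × c | Expected recorded | Chance of none |
|---|---|---|---|---|
| 10 % | 100 % | 0.100 | 2.4 | 8.0 % |
| 10 % | 75 % | 0.075 | 1.8 | 15.4 % |
| 10 % | 50 % | 0.050 | 1.2 | 29.2 % |
| 10 % | 25 % | 0.025 | 0.6 | 54.5 % |
| 20 % | 100 % | 0.200 | 4.8 | 0.5 % |
| 20 % | 75 % | 0.150 | 3.6 | 2.0 % |
| 20 % | 50 % | 0.100 | 2.4 | 8.0 % |
| 20 % | 25 % | 0.050 | 1.2 | 29.2 % |

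**The case against.** A reader might infer that tolerability rests on a single open question, that usability complaints never reach the AE data, and that local reactions are therefore undercounted. The documents support none of these.

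- Protocol 7.6 lists further sources and a general capture duty, and 7.5.2 says to report in case of doubt. SAP 6.2 also counts withdrawals from study or treatment in the tolerability assessment.
- Irritation and burning, close relatives of the expected reactions, are actively scored, including during dosing on Day 4 (and Day 11 if prolonged).
- Usability questions are asked at site visits where AEs are also recorded. A complaint of pain made there falls under the capture duty, and nothing bars its entry. The eCRF instructions, which might cover this, were not available.
- The illustration is not evidence. The 20 % ceiling comes from another product, and the documents do not say how that study elicited AEs. If it also relied on an open question, multiplying by an elicitation fraction would discount the rate twice.
- Solicitation has its own bias. Protocol 1.1 lists itching and burning among BV symptoms, so a question asked only after dosing would record persisting disease as product reactions.
- The endpoint is descriptive, in a feasibility study of 24 women, so no hypothesis test changes.

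All of these stand, and they set the limits of the point. They do not remove it: the capture duty and the doubt rule act once a complaint is known and do not draw it out, and the symptom scores cover neither itching nor insertion discomfort. The bias argument determines the form of the fix.

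**Conclusion.** The point holds as a risk. The plan does not ask specifically about the local effects it anticipates, and it states no route to AE review for two sources likely to reveal local reactions. Mild local reactions may therefore be under-recorded, in the direction that favours a co-primary endpoint which must look favourable. Whether they will be, and by how much, cannot be derived from the documents: it depends on how women answer a general question and on how sites apply the capture duty. In the table above, imperfect elicitation raises the chance of recording no reaction from 8 % to between 15 % and 54 % at a true rate of 10 %, and from 0.5 % to between 2 % and 29 % at 20 %, all under assumed fractions. The cure-rate analysis is unaffected. The change is worth making because it is cheap and the tolerability conclusion depends on this collection.

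**What to change.** - **Appendix 1, Section 4.** Keep the open question first. Then add one fixed yes/no item on itching, pain, soreness, bleeding or other vaginal discomfort, with insertion discomfort added after dosing. Record start date and severity on the scale in Protocol 7.5.1. Ask it at Day 0 before dosing and at each post-dose contact. SAP 7.1.2 places the first dose after the Day 0 visit, so that visit gives a pre-dose value. Count only complaints that are new or worse than at Day 0, so that persisting BV symptoms are not counted as reactions.
- **Review rule.** Before the clean file meeting, have the investigator review as possible AEs every physical reason given for a usability answer of no, and any single irritation or burning score above its Day 0 value. This is a review, not automatic AE entry, because a raised score may reflect the disease. It uses data already collected, so it is possible even if the questionnaire can no longer change.
- **SAP 7.10.2.** Present solicited and volunteered local events separately.

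The cost is one questionnaire item with its eCRF fields, a short review and one more table. The downside is more mild AEs on record. The Day 0 comparison limits the confusion with disease symptoms but, without a control arm, cannot remove it.
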